### 2.2 Secondary Objectives

- 2.2.1 To determine if prophylactic administration of tamsulosin reduces hospital stay or likelihood of discharge to a skilled nursing facility
- 2.2.2 To determine if prophylactic administration of tamsulosin reduces surgical site infection over two weeks, postoperatively
- 2.2.3 To determine if prophylactic administration of tamsulosin reduces acute postoperative pain medication requirements
- 2.2.4 To determine if prophylactic administration of tamsulosin reduces postoperative complications (deep venous thrombosis, pulmonary embolism, cardiovascular event, pneumonia, fevers, urinary tract infection)

### 2.3 Endpoints/Measurements

Primary endpoint of the study is the development of POUR. POUR is defined as any of the following: 1) any estimated post-void residual (PVR) volume of urine greater than or equal to 200 mL per bladder scan; 2) estimated urine volume retention of greater than or equal to 200 mL in patients unable to void within six hours after indwelling urinary catheter removal; 3) patients experiencing bladder discomfort or distention and unable to void with residual urine volume less than 200 mL; 4) requirement of intermittent straight catheterization (ISC) during hospitalization; 5) administration of tamsulosin outside of the study medication during the postoperative hospitalization. The development of POUR will be determined based on recorded values in the electronic medical record of bladder scans, the need for ISC, initiation of tamsulosin in the medication administration record, and mention of urinary retention in daily progress notes or in the discharge summary. If a patient is asymptomatic with regards to urinary symptoms and does not require intermittent urinary catheterization, but does not have any PVR volumes recorded in the medical record, then the patient is clinically deemed to not have developed POUR.

In keeping with our standard of care for arthroplasty patients who develop POUR, as defined in section 2.1.1, after the Foley catheter is discontinued, will be given a trial of intermittent straight catheterization (ISC) for 24 hours. If, after 24 hours of ISC, the patient has not resumed spontaneous voids with a residual volume of less than 200 mL,

management will be continued based on routine protocol for urinary retention after surgery (post-void bladder scan, straight urinary catheterization, possible Foley catheter placement, and possible urology consult).

Secondary measures are: length of hospital stay, incidence of discharge to a skilled nursing facility, surgical site infection, acute postoperative pain medication requirements, and other postoperative complications (deep venous thrombosis, pulmonary embolism, cardiovascular event, pneumonia, fevers, or urinary tract infection).

### 3. PATIENT ELIGIBILITY

Subjects must meet all of the inclusion and exclusion criteria requirements to be registered to the study. Study treatment may not begin until a subject is registered.

#### 3.1 Inclusion Criteria

1. Men age  $\geq$  35 years
2. Primary total hip and knee arthroplasty patients (general, spinal, or epidural anesthesia)
3. No current use (>one month) of alpha blockers
4. Community ambulator
5. Adequate organ and marrow function as defined below:
  - leukocytes  $\geq$  3,000/ $\mu$ L
  - absolute neutrophil count  $\geq$  1,500/ $\mu$ L
  - platelets  $\geq$  100,000/ $\mu$ L
  - creatinine within normal institutional limits
6. Ability to understand, and the willingness to sign, a written informed consent
7. Use of intraoperative foley.

#### 3.2 Exclusion Criteria

1. History of radical prostatectomy
2. Receiving any other investigational agents
3. Revision hip and knee arthroplasty patients
4. Severe liver or kidney disease
5. Taking strong inhibitors of CYP3A4 (ketoconazole, itraconazole, clarithromycin, ritonavir, indinavir/ritonavir, lopinavir/ritonavir, or conivaptan)
6. Being on alpha-blockers (alfuzosin, doxazosin, prazosin, terazosin, tamsulosin, phenoxybenzamine, or silodosin)
7. Being on 5-alpha reductase inhibitors (finasteride, dutasteride)
8. History of allergy or sensitivity to tamsulosin or other alpha-blockers (alfuzosin, doxazosin, prazosin, terazosin, or phenoxybenzamine)

9. Uncontrolled intercurrent illness including, but not limited to, ongoing or active infection, symptomatic congestive heart failure, unstable angina pectoris, cardiac arrhythmia, or psychiatric illness/social situations that would limit compliance with study requirements
10. Taking Sildenafil, [Tadalafil](#), or [Vardenafil](#)

##### 4.2 Toxicities and Dosing Delays/Dose Modifications

Any patient who receives treatment on this protocol will be evaluated for toxicity per the Toxicity Assessment Survey (attached). Each patient will be assessed for the development of toxicity per the Time and Events Table, and overall study cohort safety will be statistically compared at defined intervals (See Section 5.4).

#### 4.3 Concomitant Medications/Treatments

Medication contraindications include CYP3A4 inhibitors (ketoconazole, itraconazole, clarithromycin, ritonavir, indinavir/ritonavir, lopinavir/ritonavir, and conivaptan) and other medications that may have an interaction (amiodarone, dronedarone, boceprevir, chloramphenicol, clarithromycin, cobicistat, conivaptan, cyclosporine, delavirdine, doxazosin, fluvoxamine, fosamprenavir, imatinib, itraconazole, ketoconazole, lopinavir/ritonavir, nefazodone, nelfinavir, posaconazole, prazosin, rifampin/isoniazid, rifampin/isoniazid/pyrazinamide, ritonavir, telaprevir, telithromycin, terazosin, tipranavir, voriconazole), Sildenafil, Tadalafil, and Vardenafil .

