### 1.2 Study Agent(s)/Devices Background and Associated Known Toxicities

Tamsulosin has been shown to reduce POUR following radical prostatectomy (2, 3), prostate brachytherapy (4), and inguinal herniorrhaphy (5) and can increase ureteral calculi expulsion rate and speed (6, 7).

The safety of tamsulosin is well known given its selectivity for the genitourinary tract, versus blood vessels (8). Reported adverse reactions include drug allergy (contains sulfa) and floppy iris syndrome (9). Common side effects include orthostatic hypotension, dizziness, fainting, vertigo, headache, nasal congestion and palpitations.

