## 7.0 ADVERSE EVENTS

### 7.1 Experimental Therapy

- 7.1.1 *Contraindications*  
History of allergy, sulfa allergy potential for cross sensitivity, poor cyp2d6 metabolizers

7.1.2 *Special Warnings and Precautions for Use*

Floppy iris syndrome in patients undergoing cataract surgery while on Flomax

7.1.3 *Interaction with other medications (per Epocrates):*

Amiodarone, dronedarone, boceprevir, chloramphenicol, clarithromycin, cobicistat, conivaptan, cyclosporine, delavirdine, doxazosin, fluvoxamine, fosamprenavir, imatinib, itraconazole, ketoconazole, lopinavir/ritonavir, nefazodone, nelfinavir, posaconazole, prazosin, rifampin/isoniazid, rifampin/isoniazid/pyrazinamide, ritonavir, telaprevir, telithromycin, terazosin, tipranavir, voriconazole

7.1.4 *Adverse Reactions*

	All	Drug related
Any	390 (76)	132 (26)
$\alpha_1$ -adrenoceptor blocker-associated		
Dizziness	44 (8.5)	30 (5.8)
Abnormal ejaculation	25 (4.9)	22 (4.3)
Headache	24 (4.7)	7 (1.4)
Asthenia	20 (3.9)	10 (1.9)
Rhinitis	18 (3.5)	3 (0.6)
Postural hypotension	15 (2.9)	14 (2.7)

Palpitation	14 (2.7)	7 (1.4)
Dry mouth	8 (1.6)	6 (1.2)
Syncope	5 (1.0)	0
Somnolence	4 (0.8)	2 (0.4)
Other		
Impotence	28 (5.4)	15 (2.9)
Decreased libido	6 (1.2)	4 (0.8)
Urinary retention	23 (4.5)	1 (0.2)
Discontinued treatment	86 (217)	26(5)

Others: allergic reaction, angioedema, Steven Johnson syndrome, arrhythmia, priapism (10)

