### **11.3 Registration Procedures**

All patients must be registered before enrollment to study. Prior to registration, eligibility criteria must be confirmed with the study coordinator.

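### Section 3.2 omits two conditions that 7.1.1 lists as contraindications, and leaves it unclear whether up to 19 drugs listed in 4.3 are barred

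*Combined protocol and SAP*

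**What the plan says.** **Conditions.** Section 7.1.1, under contraindications, reads "History of allergy, sulfa allergy potential for cross sensitivity, poor cyp2d6 metabolizers". The background in 1.2 makes the same link: "Reported adverse reactions include drug allergy (contains sulfa". The only allergy criterion in 3.2 is exclusion 8: "History of allergy or sensitivity to tamsulosin or other alpha-blockers (alfuzosin, doxazosin, prazosin, terazosin, or phenoxybenzamine". Neither 3.1 nor 3.2 mentions sulfa or CYP2D6.

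**Drugs.** Section 4.3 gives three groups in one sentence: CYP3A4 inhibitors, a longer list of other drugs, and three PDE5 inhibitors. It introduces them with "Medication contraindications include CYP3A4 inhibitors (ketoconazole, itraconazole, clarithromycin, ritonavir, indinavir/ritonavir, lopinavir/ritonavir, and conivaptan) and other medications that may have an interaction". In 3.2, exclusion 5 reads "Taking strong inhibitors of CYP3A4 (ketoconazole, itraconazole, clarithromycin, ritonavir, indinavir/ritonavir, lopinavir/ritonavir, or conivaptan", exclusion 6 names alpha-blockers, and exclusion 10 begins "Taking Sildenafil" and goes on to tadalafil and vardenafil. Sections 7.1.3 and 8.1 repeat the longer list from 4.3, headed as interactions and as incompatibilities.

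**What governs entry.** Section 3 states "Subjects must meet all of the inclusion and exclusion criteria requirements to be registered to the study", and 11.3 states "Prior to registration, eligibility criteria must be confirmed with the study coordinator".

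**The concern.** The protocol states in one place who should not receive tamsulosin and in another who may not be registered, and the two do not match. An eligibility checklist that follows section 3 faithfully would pass a man with a sulfa allergy. It could also pass a man taking a drug that 4.3 places under contraindications.

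The screening check matters because dosing starts at home. Section 4.1 schedules five capsules before surgery and one on the morning of surgery, so 5 + 1 = 6 of the 7 are due before the survey on postoperative day one. Adverse events are monitored under 7.2, but screening is the main point at which such a man can be kept from starting the drug.

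What is at stake is participant safety and consistent conduct, not the primary comparison.

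**Working it through.** The plan gives no figure on this point, so the check is a comparison of lists.

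**Conditions (7.1.1 against 3.1 and 3.2)**
- History of allergy: covered by exclusion 8 for tamsulosin and other alpha-blockers.
- Sulfa allergy: not named. Exclusion 8 does not reach it, because a sulfa-allergic man who has never taken an alpha-blocker has no such reaction to report.
- Poor CYP2D6 metabolism: not named. The screening procedures in 5.1 include no check of it.

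Two of the listed contraindicating conditions therefore have no matching exclusion.

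**Drugs (4.3 against 3.2), counted by entry**
- Entries in 4.3: 7 CYP3A4 inhibitors + 28 other drugs + 3 PDE5 inhibitors = 38.
- Repeats: 6 of the 28 already stand in the CYP3A4 group (clarithromycin, conivaptan, itraconazole, ketoconazole, lopinavir/ritonavir, ritonavir). Distinct names: 38 − 6 = 32.
- Named in 3.2: 7 (exclusion 5) + 3 (exclusion 6: doxazosin, prazosin, terazosin) + 3 (exclusion 10) = 13.
- Not named: 32 − 13 = 19.

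| Group in 4.3 | Distinct names | Named in 3.2 |
|---|---|---|
| CYP3A4 inhibitors | 7 | 7 |
| Other drugs, repeats removed | 28 − 6 = 22 | 3 |
| PDE5 inhibitors | 3 | 3 |

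The 19 are amiodarone, boceprevir, chloramphenicol, cobicistat, cyclosporine, delavirdine, dronedarone, fluvoxamine, fosamprenavir, imatinib, nefazodone, nelfinavir, posaconazole, the two rifampin combinations, telaprevir, telithromycin, tipranavir and voriconazole.

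The count depends slightly on how combinations are treated. Merging the two rifampin products gives 18; splitting every combination into its substances gives 20 unnamed of 33.

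**Do the labels settle the status of the 19?** No. The lists in 7.1.3 and 8.1 hold the same 28 names. Of these, 6 + 3 = 9 are excluded by name in 3.2 and 28 − 9 = 19 are not. Barred and unbarred drugs stand together under the milder headings there and under the stronger one in 4.3. Neither label separates them.

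**Safeguards after registration.** Item 2 of 4.4 ends therapy once an adverse reaction to tamsulosin occurs. Section 5.5 allows removal for inability to comply, for toxicity, or on the physician's judgement, and 4.6 keeps the man in follow-up. None names sulfa allergy, CYP2D6 status or any of the 19 drugs as a trigger, and 4.4(2) acts only after a reaction.

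**The case against.** The strongest reply is that the protocol must be read as a whole. Section 4.3 belongs to the treatment plan, and 11.5 requires the study to be run as the protocol describes, so giving capsules to a man on a contraindicated drug would already be a departure. Screening reviews medical history (5.1.2) and medications (5.1.5) separately from the eligibility review (5.1.4). An attentive clinician would see the problem, and 5.5.3 could be used to stop a man who needs a 4.3 drug.

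The drug list may also be tiered on purpose. The long group is described only as drugs that may interact, so the authors may have meant to exclude the clearest hazards and leave the rest to judgement. Exclusion 5 opens with a class, strong CYP3A4 inhibitors, which may already cover some of the 19. Exclusion 9 bars uncontrolled illness, including active infection and cardiac arrhythmia, and so may catch men who take a listed drug for such an illness.

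Much of this stands for the drugs. A reader might infer that 19 contraindicated drugs are open to enrolled men. The documents do not support that: some may be excluded by class, some users by exclusion 9, and others may have been meant as cautions. What remains is that the text does not say which.

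Little of it stands for sulfa allergy. There is no class wording to fall back on, 7.1.1 uses the plain heading of contraindications, and protection rests on someone looking beyond the criteria that registration requires. For CYP2D6 the practical gain is limited, because status will often be unknown without a test.

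**Conclusion.** The concern holds in two parts of unequal strength. The firm part is that two conditions listed as contraindications in 7.1.1 have no matching criterion, so registration under section 3 as written can admit a man whom the protocol itself calls contraindicated. The softer part is that up to 19 of the 32 drug names in 4.3 have an unclear status. The true gap is smaller if exclusion 5 is a class, and by an amount the documents do not let one compute.

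A reader might also want the number of men affected, or the chance that at least one is enrolled. The documents give no prevalence for either condition or for use of these drugs. Any such figure would only restate an assumed prevalence together with an assumption that screening catches no one, and it would measure enrolment, not harm.

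The sample size in 10.2 (91 per arm, 114 with allowance for loss, 228 in total), the power and alpha are unaffected. This is a safety and consistency point that merits an amendment; it does not threaten the primary inference.

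**What to change.** 1. Add sulfa allergy to 3.2.
2. Add previously known poor CYP2D6 metaboliser status to 3.2, with no new testing.
3. State whether exclusion 5 is a class with examples or a closed list.
4. Have the study clinicians mark each remaining drug in 4.3 either as excluded, and add it to 3.2, or as caution only, and relabel it in 4.3. Sections 3.2, 4.3, 7.1 and 8.1 should then agree.

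The cost is a wording amendment, IRB approval under 11.6 and an updated eligibility checklist. Screening already collects the history and medications needed, so no procedure is added. The downside is a few more screen failures, and so somewhat more than the planned 456 screened to reach 228 enrolled; the number cannot be derived from the documents. Poor metabolisers whose status is unknown would still enrol.

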#### 4.4 Duration of Therapy

End of protocol therapy occurs when 1) patient completes the seven-capsule regimen, 2) adverse reaction to tamsulosin occurs, 3) postoperative complication occurs; deemed prohibitive of further continuation of therapy, 4) patient decides to withdraw, 5) an indwelling catheter is placed for monitoring the fluid and electrolyte intake and output for medical purpose, 6) patient perishes.

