#### 4.6 Removal of Patients from Protocol Therapy

Patients will be removed from therapy when any of the criteria listed in Section 5.5 apply. The Principal Investigator will be notified, and the reason for therapy removal and the date the patient was removed will be documented on the Case Report Form. The patient should be followed-up per protocol.

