**5.2.3 Post-discharge**

[figure not shown]
Patients that go on to treatment failure will be discharged with a plan of care dictated by urology (if consulted), or the primary treatment team, which may include Foley catheter placement, tamsulosin, intermittent straight catheterization, outpatient follow-up with urologist or primary care physician, or some combination of the previously mentioned treatment options.

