**10.2 Sample Size and Accrual**

POUR occurs in approximately 40% of patients following primary total hip or knee arthroplasty. Risk factors for POUR include male sex, total hip arthroplasty, intrathecal morphine and epidural anesthesia. A sample size of 91 in each arm (tamsulosin versus placebo) is needed with continuity correction if a reduction of 50% (or a POUR incidence of 20%) is to be detected with a power of 80% at a significance level of  $\alpha < 0.05$ . 114 patients are need in each arm assuming an accrual rate of 80% for a total of 228 patients.

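### The no-PVR default in section 2.3 does not require a voiding opportunity, so a man catheterised until discharge is scored free of POUR; criterion 4 also omits Foley re-insertion

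*Combined protocol and SAP*

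**What the plan says.** **Endpoint.** Section 2.3 of the combined protocol and SAP lists five alternative criteria for POUR:

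1. a PVR of 200 mL or more on bladder scan;
2. retained volume of 200 mL or more in a man unable to void within six hours of catheter removal;
3. discomfort or distension with inability to void and a residual below 200 mL;
4. "requirement of intermittent straight catheterization (ISC) during hospitalization";
5. non-study tamsulosin given during the postoperative stay.

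The chart sources include scans, straight catheterisation (ISC), the medication record, and mentions of retention in progress notes or the discharge summary. A default follows. A man without urinary symptoms who "does not require intermittent urinary catheterization, but does not have any PVR volumes recorded in the medical record" is deemed not to have developed POUR.

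**Catheters.** Section 4.1.3 gives every man an intraoperative Foley, due out on the morning of postoperative day one. Section 4.4 ends protocol therapy if "an indwelling catheter is placed for monitoring the fluid and electrolyte intake and output for medical purpose". Section 4.6 says of men removed from therapy: "The patient should be followed-up per protocol". It points to the criteria in section 5.5, which do not include the monitoring catheter.

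**Rescue.** Section 2.3 describes a 24-hour ISC trial for men who develop POUR, with possible Foley placement afterwards. Section 5.2.3 describes a discharge plan for treatment failure "which may include Foley catheter placement, tamsulosin, intermittent straight catheterization", among other options. Section 4.5 allows discharge on tamsulosin after treatment failure and says that this will be noted. Treatment failure is not defined.

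**The concern.** The default converts absence of evidence into a recorded success. That is reasonable for a man whose catheter is out and who voids without trouble. It is not reasonable for a man whose bladder is being drained. An indwelling catheter tends to bring about all three conditions of the default at once: no retention symptoms, no need for ISC and no post-void residual to scan. The six-hour clock in criterion 2 does not start until the catheter is removed.

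The timing makes the case realistic. The scheduled catheter removal and the last scheduled capsule both fall on postoperative day one, and section 4.5 puts the average stay at 1 to 4 days. A monitoring catheter that cuts the regimen short may therefore displace the voiding trial.

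The second gap runs the other way. A man whose Foley is put straight back because he cannot void has retention in the ordinary sense, yet re-insertion is not among the five criteria.

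At stake is misclassification of the primary endpoint. If it is equal in both arms, it shrinks the risk difference and costs power. If it is unequal, it shifts the comparison towards the arm with more unassessed men. Section 10.3 has no rule for a missing primary outcome that would correct this.

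**Working it through.** **A. Monitoring catheter: 4.4 against 2.3.** There are three cases.

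- *Voiding assessed before the catheter was placed* (for example, after the day-one removal): that assessment can be scored under criteria 1 to 3.
- *Catheter out again before discharge:* criteria 1 to 3 apply from then on.
- *Catheter in place without a break until discharge:* no voiding attempt, no PVR, no ISC. If he has no urinary symptoms, the default is met and he is scored POUR-free.

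Only the third case is misclassified by the wording.

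**B. Foley re-insertion: the five criteria.** On the described pathway ISC comes first, so a later Foley belongs to a man who already meets criterion 4. A scan of 200 mL or more meets criterion 1 or 2, and inability to void with discomfort or distension meets criterion 3. The man who meets none is re-catheterised directly, without ISC, a qualifying scan, discomfort or distension, or in-hospital non-study tamsulosin. A chart mention of retention might still catch him, but section 2.3 lists that as a source and not as a criterion.

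**C. Illustrative size.**

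Inputs from section 10.2: "POUR occurs in approximately 40% of patients following primary total hip or knee arthroplasty"; "if a reduction of 50% (or a POUR incidence of 20%) is to be detected with a power of 80" per cent; "A sample size of 91 in each arm (tamsulosin versus placebo) is needed with continuity correction". Alpha is 0.05 (10.3), two-sided (Study Summary).

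*The plan's figure.* Without correction, n' = [1.960·√(2·0.30·0.70) + 0.842·√(0.40·0.60 + 0.20·0.80)]² / 0.20² = (1.270 + 0.532)² / 0.04 ≈ 81.2, so 82. With correction, n = (n'/4)·[1 + √(1 + 4/(n'·0.20))]² ≈ 91. This reproduces the stated 91 per arm, and 91/0.80 = 113.75 gives the stated 114.

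*Power at n = 91, corrected:* Φ{[d − 1/n − 1.960·√(2p̄(1−p̄)/n)] / √[(p₁(1−p₁) + p₂(1−p₂))/n]}, where d = p₁ − p₂ and p̄ is the mean of p₁ and p₂. At 40% v 20%: (0.2000 − 0.0110 − 0.1332)/0.0663 = 0.843, so 80.0%.

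*Missed cases.* Let a share m of true cases be scored POUR-free in both arms, giving rates 0.40(1−m) and 0.20(1−m). The same formula covers a share m of men left unassessed, if their underlying risk equals that of the others. The documents give no value for m; those below are assumptions.

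| m | Rates | Corrected power | n per arm for 80% |
|---|---|---|---|
| 0 | 40.0% v 20.0% | 80.0% | 91 |
| 2% | 39.2% v 19.6% | 78.8% | 94 |
| 5% | 38.0% v 19.0% | 76.8% | 98 |

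At m = 5%, 91 × 0.05 ≈ 4.6 men per arm are affected. This hides 4.55 × 0.40 ≈ 1.8 placebo events and 4.55 × 0.20 ≈ 0.9 tamsulosin events.

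*Unequal shares.* Suppose there is no true effect (40% in both arms) and the tamsulosin arm has 5 percentage points more unassessed men. The false benefit is 0.05 × 0.40 = 2 points, and two-sided rejection rises from 5% to about 5.9% (uncorrected test).

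**The case against.** The other side has several sound points.

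- **A reader might infer that a man with a monitoring catheter never has a voiding trial and is always scored POUR-free.** The documents do not say so. The catheter may be placed after voiding was tested, or may come out before discharge. The default also needs all three of its conditions. This stands, and confines the problem to men catheterised until discharge with no earlier assessment.
- **A reader might infer that Foley rescue generally goes uncounted.** It does not: the described pathway tries ISC first, and retention noted in the chart is a stated source. Men discharged on rescue for treatment failure would usually already be events. This stands too; what remains is the directly re-catheterised man in B.
- **A reader might infer that hypotension on tamsulosin would produce extra monitoring catheters and hence false efficacy.** The table in section 7.1.4 gives drug-related postural hypotension of 2.7% and drug-related syncope of 0, with no placebo column. Even if every such man kept a monitoring catheter to discharge, that is 0.027 × 91 ≈ 2.5 men, and 0.027 × 0.40 ≈ 1.1 points of false benefit at a 40% rate. Imbalance is possible but not shown.
- **Power.** Section 10.3 names a chi-square test without mentioning a correction. Uncorrected power is 84.3% at the design rates and 81.6% with 5% of cases missed. Equal under-counting leaves the risk ratio at 0.5.
- **Dropping unassessed men is not neutral either.** It removes randomised men on a post-treatment event and recovers little power: 77.7% against 76.8% at 5%. This is why the fix keeps them in the randomised set.

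None of this supplies the missing scoring rule.

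**Conclusion.** The concern holds in limited form. As worded, section 2.3 scores as a success an asymptomatic man who keeps a catheter until discharge and was never assessed, and section 4.4 shows that monitoring catheters are foreseen. Criterion 4 leaves a narrow gap for direct Foley re-insertion.

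The size is unknown and probably small. The power figures (80.0% to 78.8% or 76.8%) illustrate assumed shares of 2% and 5%, equal in both arms. They are not estimates. A false benefit needs unequal shares, for which the documents offer plausibility and no evidence. The sample-size arithmetic is unaffected.

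The wording is still worth correcting, because it is an implicit missing-data rule inside the primary endpoint and the correction is cheap. The cross-references also need repair: 2.1.1 lists three criteria against five in 2.3, and 4.5 and 4.6 refer to 5.5 for criteria that include the monitoring catheter only in 4.4.

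**What to change.** Change the scoring rules only, and settle them before unblinding. In section 2.3:

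1. Limit the deemed-no-POUR sentence to men whose catheter was removed and who had an opportunity to void before discharge.
2. Score a man with a monitoring catheter on any voiding assessment before or after it. If there is none, keep him in the randomised set as outcome missing, run sensitivity analyses counting him as POUR and as no POUR, and report the number of such men by arm. Add the handling to section 10.3.
3. Count any in-hospital re-catheterisation for failure to void, including Foley, under criterion 4.
4. State whether a chart mention of retention alone makes an event, and whether discharge on tamsulosin for retention (already noted under 4.5) does.

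Reconcile the endpoint lists in 2.1.1 and 2.3, and the end-of-therapy criteria in 4.4 with the references to 5.5 in 4.5 and 4.6.

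The cost is endpoint wording and a little more abstraction from the chart review already planned. The downside is that a few men will have a missing primary outcome. No change to catheter use, dosing or rescue care is proposed.
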